**APPENDIX F EQ-5D-5L (V.2)**

Subjects should be instructed to fill out the EQ-5D-5L (v.2) questionnaire to the best of their abilities. The study staff will be responsible for confirming that the subject has completed the questionnaire.

Approved

---

CONFIDENTIAL

**APPENDIX G EASTERN COOPERATIVE ONCOLOGY GROUP (ECOG)  
PERFORMANCE SCALE**

Grade	Description
0	Normal activity, fully active, able to carry on all predisease performance without restriction.
1	Symptoms, but fully ambulatory, restricted in physically strenuous but ambulatory and able to carry out work of a light or sedentary nature (e.g., light housework, office work).
2	Ambulatory and capable of all self-care but unable to carry out any work activities. Up and about more than 50% of waking hours.
3	Capable of only limited self-care, confined to bed or chair more than 50% of waking hours.
4	Completely disabled. Cannot carry on any self care. Totally confined to bed or chair.
5	Death

Source: [Oken 1982](#)

Eastern Cooperative Oncology Group, [name] M.D., Group Chair

Approved

CONFIDENTIAL

**APPENDIX H DRUG-DRUG INTERACTION POTENTIAL OF OPROZOMIB  
AND POMALIDOMIDE**

**Oprozomib**

Alfentanil	Diergotamine	Quinidine
Astemizole a	Ergotamine	Sirolimus
Cisapride a	Fentanyl	Tacrolimus
Cyclosporine	Pimozide	Terfenadine a

a Not available in the United States.

Because oprozomib is a P-gp substrate, use of P-gp inhibitors and inducers (see table below) should be carefully monitored and such drugs should be substituted for others if necessary.

**Pomalidomide**

In accordance with the Pomalidomide Prescribing Information, use of the following concomitant medications is to be carefully monitored and these drugs should be substituted for others if necessary.

***Drugs That May Increase Pomalidomide Plasma Concentrations***

CYP3A, CYP1A2, or P-gp inhibitors: Co-administration of POMALYST with drugs that are strong inhibitors of CYP1A2, CYP3A (e.g., ketoconazole) or P-gp could increase exposure and should be avoided.

***Drugs That May Decrease Pomalidomide Plasma Concentrations***

CYP3A, CYP1A2, or P-gp inducers: Co-administration of POMALYST with drugs that are strong inducers of CYP1A2, CYP3A (e.g., rifampin) or P-gp could decrease exposure and should be avoided.

***Smoking***

Cigarette smoking may reduce pomalidomide exposure due to CYP1A2 induction. Subjects should be advised that smoking may reduce the efficacy of pomalidomide.

Approved

Onyx Therapeutics  
 Oprozomib ER Tablets

Clinical Study Protocol No. OPZ007  
 Page 137 of 223

The tables below provide lists of the inhibitors and inducers of concern.

CYP 3A inhibitor	CYP1A2 inhibitor	P-gp inhibitor
Strong:	Strong:	
boceprevir clarithromycin conivaptan grapefruit juice indinavir itraconazole ketoconazole lopinavir/ritonavir mibefradil nefazodone nelfinavir posaconazole ritonavir saquinavir telaprevir, telithromycin, voriconazole	ciprofloxacin enoxacin fluvoxamine	amiodarone azithromycin captopril carvedilol clarithromycin conivaptan cyclosporine diltiazem dronedarone erythromycin felodipine itraconazole ketoconazole lopinavir and ritonavir quercetin quinidine, ranolazine, ticagrelor, verapamil

CYP 3A inducer	CYP1A2 inducer	P-gp inducer
Strong:		
avasimibe carbamazepine phenytoin rifampin St. John's wort		avasimibe carbamazepine phenytoin rifampin St John's wort tipranavir/ritonavir

Approved

CONFIDENTIAL

## APPENDIX I POMALIDOMIDE RISKS OF FETAL EXPOSURE, PREGNANCY TESTING GUIDELINES, AND ACCEPTABLE BIRTH CONTROL METHODS

### Risks Associated with Pregnancy

Pomalidomide was found to be teratogenic in a developmental study in rabbits.

Pomalidomide is an analogue of thalidomide. Thalidomide is a known human teratogen that causes severe life-threatening human birth defects. If pomalidomide is taken during pregnancy, it may cause birth defects or death to an unborn baby.

### Criteria for Females of Childbearing Potential (FCBP)

This protocol defines a female of childbearing potential as a sexually mature woman who: 1) has not undergone a hysterectomy or bilateral oophorectomy or 2) has not been naturally postmenopausal (amenorrhea following cancer therapy does not rule out childbearing potential) for at least 24 consecutive months (i.e., has had menses at any time in the preceding 24 consecutive months).

### Counseling

For an FCBP, pomalidomide is contraindicated unless all of the following are met (i.e., FCBP must be counseled concerning the following risks and requirements prior to the start of pomalidomide study therapy):

- She understands the potential teratogenic risk to the unborn child
- She understands the need for effective contraception, without interruption, 28 days before starting study treatment, throughout the entire duration of study treatment, dose interruption, and 28 days after the End of Study Treatment
- She should be capable of complying with effective contraceptive measures
- She is informed and understands the potential consequences of pregnancy and the need to notify her study doctor immediately if there is a risk of pregnancy
- She understands the need to commence the study treatment as soon as pomalidomide is dispensed following a negative pregnancy test
- She understands the need and accepts to undergo pregnancy testing based on the frequency outlined in this protocol
- She acknowledges that she understands the hazards and necessary precautions associated with the use of pomalidomide

Approved

CONFIDENTIAL

**The Investigator must ensure that females of childbearing potential:**

- Comply with the conditions for pregnancy risk minimization, including confirmation that she has an adequate level of understanding
- Acknowledge the aforementioned requirements

For a female NOT of childbearing potential, pomalidomide is contraindicated unless the following are met (i.e., all females NOT of childbearing potential must be counseled concerning the following risks and requirements prior to the start of pomalidomide study therapy):

- She acknowledges that she understands the hazards and necessary precautions associated with the use of pomalidomide

The effect of pomalidomide on spermatogenesis is not known and has not been studied.

Therefore, male subjects taking pomalidomide must meet the following conditions (i.e., all males must be counseled concerning the following risks and requirements prior to the start of pomalidomide study therapy):

- Understand the potential teratogenic risk if engaged in sexual activity with a woman of childbearing potential
- Understand the need for the use of a condom, even if he has had a vasectomy, if engaged in sexual activity with a female of childbearing potential.

**Contraception**

Females of childbearing potential enrolled in this protocol must agree to use 2 reliable forms of contraception simultaneously or to practice complete abstinence from heterosexual intercourse during the following time periods related to this study: 1) for at least 28 days before starting study drug; 2) while participating in the study; 3) dose interruptions; and 4) for at least 28 days after study treatment discontinuation.

The 2 methods of reliable contraception must include 1 highly effective method and 1 additional effective (barrier) method. An FCBP must be referred to a qualified provider of contraceptive methods if needed.

Approved

The following are examples of highly effective and additional effective methods of contraception:

- Highly effective methods:
  - Intrauterine device (IUD)
  - Hormonal (birth control pills, injections, implants)
  - Tubal ligation
  - Partner's vasectomy
- Additional effective methods:
  - Male condom
  - Diaphragm
  - Cervical cap

Because of the increased risk of venous thromboembolism in patients with multiple myeloma taking pomalidomide and dexamethasone, combined oral contraceptive pills are not recommended. If a subject is currently using combined oral contraception the subject should switch to another one of the effective methods listed above. The risk of venous thromboembolism continues for 4–6 weeks after discontinuing combined oral contraception.

The efficacy of contraceptive steroids may be reduced during co-treatment with dexamethasone.

Implants and levonorgestrel-releasing intrauterine systems are associated with an increased risk of infection at the time of insertion and irregular vaginal bleeding. Prophylactic antibiotics should be considered, particularly in subjects with neutropenia.

### **Pregnancy testing**

Medically supervised pregnancy tests with a minimum sensitivity of 50 mIU/mL must be performed for females of childbearing potential, including females of childbearing potential who commit to complete abstinence, as outlined below.

Approved

**Before starting study drug**

***Female Subjects***

Females of childbearing potential must have 2 negative pregnancy tests (sensitivity of at least 50 mIU/mL) prior to starting pomalidomide. The first pregnancy test must be performed within 10-14 days prior to the start of pomalidomide and the second pregnancy test must be performed within 24 hours prior to the start of pomalidomide. The subject may not receive study drug until the investigator has verified that the results of these pregnancy tests are negative.

***Male Subjects***

Must practice complete abstinence or agree to use a condom during sexual contact with FCBP while participating in the study, during dose interruptions, and for at least 90 days following study drug discontinuation, even if he has undergone a successful vasectomy.

**During study participation and for 28 days following study drug discontinuation**

***Female Subjects***

- Females of childbearing potential with regular or no menstrual cycles must agree to have pregnancy tests weekly for the first 28 days of study participation and then every 28 days while on study, at study discontinuation, and at Day 28 following study drug discontinuation. If menstrual cycles are irregular, the pregnancy testing must occur weekly for the first 28 days and then every 14 days while on study, at study discontinuation, and at Days 14 and 28 following study drug discontinuation.
- At each visit, the investigator must confirm with the FCBP that she is continuing to use 2 reliable methods of birth control.
- Counseling about pregnancy precautions and the potential risks of fetal exposure must be conducted at a minimum of every 28 days.
- If pregnancy or a positive pregnancy test does occur in a study subject, pomalidomide must be immediately discontinued.
- Pregnancy testing and counseling must be performed if a subject misses her period or if her pregnancy test or her menstrual bleeding is abnormal. Study drug treatment must be discontinued during this evaluation.
- Females must agree to abstain from breastfeeding during study participation and for at least 28 days after study drug discontinuation.

Approved

Onyx Therapeutics  
Oprozomib ER Tablets

Clinical Study Protocol No. OPZ007  
Page 142 of 223

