### 10.6.1 REQUIRED CONCOMITANT MEDICATIONS

#### 10.6.1.1 Contraception

Females of reproductive potential must commit either to abstain continuously from heterosexual sexual intercourse or to use 2 methods of effective contraception simultaneously (1 highly effective form of contraception—tubal ligation, intrauterine device [IUD], hormonal [birth control pills, injections, hormonal patches, vaginal rings or implants] or partner's vasectomy and 1 additional effective contraceptive method—male latex or synthetic condom, diaphragm, or cervical cap). Contraception must begin 4 weeks prior to initiating treatment and continue during therapy, dose interruptions, and for 28 days after discontinuation of therapy. Reliable contraception is indicated even where there has been

Approved

CONFIDENTIAL

a history of infertility, unless this is due to hysterectomy. Females of reproductive potential should be referred to a qualified provider of contraceptive methods, if needed. Additional details are provided in Pomalidomide Risks of Fetal Exposure, Pregnancy Testing Guidelines and Acceptable Birth Control Methods ([Appendix J](#)), Pomalidomide Education and Counseling Guidance Document ([Appendix K](#)), and Pomalidomide Information Sheet for Subjects Enrolled in Clinical Research Studies ([Appendix L](#)).

Females of reproductive potential must have 2 negative pregnancy tests before initiating study treatment. The first test should be performed within 10–14 days of study treatment and the second test should be performed within 24 hours before study treatment. Once treatment has started and during dose interruptions, pregnancy testing for female subjects of reproductive potential should occur weekly during the first 4 weeks of treatment. Pregnancy testing should be repeated every 4 weeks thereafter for female subjects with regular menstrual cycles. For female subjects with irregular menstrual cycles ( $\pm 7$  days of a 28-day cycle), pregnancy testing should be performed every 2 weeks. Pregnancy testing and counseling should be performed if a subject misses her period or if there is any abnormality in her menstrual bleeding. Study treatment must be discontinued during this evaluation.

Postmenopausal females ( $> 45$  years old and without menses for  $> 2$  years) and surgically sterilized females are exempt.

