## **11 STUDY PROCEDURES**

All protocol-required tests and observations, along with their chronology, are outlined in the Schedules of Assessments ([Appendices A1, A2, B1, and B2](#)). A general summary of on-treatment tests and observations is provided below.

---

CONFIDENTIAL

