### **11.2.4 PREGNANCY**

For females of childbearing potential (FCBP), both a serum pregnancy test that is confirmed negative at Screening and a serum pregnancy test that is confirmed negative within 24 hours prior to Day 1 of each cycle is required prior to dosing. For the first cycle, negative pregnancy tests are required weekly. Starting with the second cycle, a negative pregnancy test monthly is required. For FBCP subjects with irregular menses (ie, other than  $28 \pm 7$  days) or whose menses are not present, a negative pregnancy test every other week is required. More frequent pregnancy tests may be conducted if required according to local regulations.

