**APPENDIX A1 SCHEDULE OF STUDY ASSESSMENTS – PHASE 1B DOSE ESCALATION 5/14 SCHEDULE (CONT'D)**

-  Coagulation tests, done locally **if clinically indicated**, and includes the following: Prothrombin time, activated partial thromboplastin time, and international normalized ratio.
- m Screening pregnancy testing, done locally, for females of childbearing potential (FCBP) must have a sensitivity of at least 50 mIU/mL with TWO medically supervised tests performed before pomalidomide dosing starts. One test must be obtained within 10–14 days and one test within 24 hours prior to the start of pomalidomide on Cycle 1 Day 1. A medically supervised, serum pregnancy test will be done weekly during Cycle 1 (Days 1, 8, 15, and 22). Starting with Cycle 2, serum pregnancy tests will be done within 24 hours prior to each cycle of pomalidomide dosing in FCBP only. Pregnancy tests will be repeated on Day 15 of Cycle 2 and beyond if menses are irregular (i.e., not within  $\pm 7$  days of a 28-day cycle) or menses are not present in FCBP.
- n Results for SPEP, UPEP, and SFLC, obtained locally, during Screening must be available before starting study drug treatment. When the subject is on study drug, the disease response assessments will be performed at the end of each cycle (Day 22–28 or prior to dosing on Day 1 of the next cycle) for the first 18 months (Cycles 1–18), then every 8 weeks thereafter (starting with Cycle 20). If the subject comes off study for reasons other than progressive disease, then disease response assessments will be performed every 4 weeks through 18 months on study, and then every 8 weeks thereafter. Obtain blood for SPEP (please refer to [Section 11.3](#) for collection times for SPEP Immunofixation, UPEP and UPEP Immunofixation with 24-hr urine, and sFLC) within 7 days prior to next Cycle study drug dosing. If a response assessment indicates PD, confirmation of PD may be obtained any time at or before the next scheduled assessment.

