**FCBP**

**1. I verified that the required pregnancy tests performed are negative.**

**2. I counseled FCBP regarding the following:**

- Potential fetal harm: If pomalidomide is taken during pregnancy, it may cause birth defects or death to any unborn baby. Females are advised to avoid pregnancy while taking pomalidomide. The teratogenic potential of pomalidomide in humans cannot be ruled out. Females of childbearing potential must agree not to become pregnant while taking pomalidomide.

Approved

CONFIDENTIAL

- Using TWO reliable methods of birth control at the same time or complete abstinence from heterosexual intercourse [at least 28 days prior, while taking pomalidomide, during dose interruption, and 28 days after discontinuation of pomalidomide].
- Continuation of TWO reliable methods of birth control or complete abstinence if therapy is interrupted.
- That even if she has amenorrhea she must comply with advice on contraception.
- Use of one highly effective method and one additional method of birth control AT THE SAME TIME. The following are examples of highly effective and additional effective methods of contraception:
  - Highly effective methods:
    - Intrauterine device (IUD)
    - Hormonal (birth control pills, injections, implants)
    - Tubal ligation
    - Partner’s vasectomy
  - Additional effective methods:
    - Male condom
    - Diaphragm
    - Cervical cap
- Pregnancy tests before and during treatment, even if the patient agrees not to have reproductive heterosexual intercourse. Two pregnancy tests will be performed prior to receiving study drug, one within 10–14 days and the second within 24 hours of the start of pomalidomide.
- Frequency of pregnancy tests to be done:
  - Every week during the first 28 days of this study and a pregnancy test every 28 days during the patient’s participation in this study if menstrual cycles are regular or every 14 days if cycles are irregular.
  - If the patient missed a period or has unusual menstrual bleeding.
  - When the patient is discontinued from the study and at Day 28 after study drug discontinuation if menstrual cycles are regular. If menstrual cycles are irregular, pregnancy tests will be done at discontinuation from the study and at Days 14 and 28 after study drug discontinuation.
- Stop taking pomalidomide immediately in the event of becoming pregnant and to call their study doctor as soon as possible.
- NEVER share pomalidomide with anyone else.

Approved

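### Appendix I tests women of childbearing potential without menses every 28 days, while Section 11.2.4 and all four assessment schedules require every 14 days from Cycle 2

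*Protocol*

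**What the plan says.** The protocol gives pregnancy-test intervals in several places.

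- **Appendix I, testing during study participation, female subjects.** "Females of childbearing potential with regular or no menstrual cycles must agree to have pregnancy tests weekly" for the first 28 days. After that this group is tested every 28 days, at study discontinuation, and at Day 28 after the drug is stopped. Women with irregular cycles are tested every 14 days, and at Days 14 and 28 after the drug is stopped.
- **Section 11.2.4.** For women with irregular menses "or whose menses are not present, a negative pregnancy test every other week is required".
- **Footnote m of Appendices A1, A2, B1 and B2.** A serum test is done within 24 hours before each cycle. It is repeated on Day 15 of Cycle 2 and later if menses are irregular "or menses are not present in FCBP".
- **Section 10.6.1.1.** "Pregnancy testing should be repeated every 4 weeks thereafter for female subjects with regular menstrual cycles", and every 2 weeks for irregular cycles.
- **Appendix J, counselling on test frequency.** Every 28 days "if menstrual cycles are regular or every 14 days if cycles are irregular".
- **Section 11.** "All protocol-required tests and observations, along with their chronology, are outlined in the Schedules of Assessments".

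The protocol expects to enrol women of childbearing potential who have no menses. The definition in Appendix I notes that "amenorrhea following cancer therapy does not rule out childbearing potential", and Appendix J includes the counselling point "That even if she has amenorrhea she must comply with advice on contraception".

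**The concern.** The same woman has two different mandatory intervals. Without menses, she belongs with regular cycles under Appendix I and with irregular cycles under Section 11.2.4 and the schedules. A site could reasonably work from Appendix I. Its title names it as the pregnancy-testing guideline, and Section 10.6.1.1 sends the reader to a document of that title for detail, although under the outdated letter J.

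Appendix I describes pomalidomide as teratogenic in rabbits and as an analogue of a known human teratogen. It also requires a test when a period is missed, but that trigger cannot work in a woman who has no periods. For her, scheduled testing is the main route to detection, and Appendix I gives her the longer interval. All subjects have had at least two prior lines of therapy, and expansion subjects also need prior alkylator treatment, so amenorrhea after cancer therapy is a realistic situation in this population.

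**Working it through.** No sample size, power or error rate is involved. The check compares the texts and then counts days, tests and doses.

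**Rules for a woman of childbearing potential without menses**

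| Location | Cycle 1 | Cycle 2 onward | After discontinuation |
|---|---|---|---|
| Appendix I | weekly | every 28 days | Day 28 |
| Section 11.2.4 | weekly | every other week | not specified |
| Footnote m, A1/A2/B1/B2 | weekly | before Day 1, and Day 15 | not specified |
| Section 10.6.1.1 | weekly | absent menses not named | not specified |
| Appendix J | weekly | absent menses not named | absent menses not named |

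Cycle 1 agrees everywhere, so the conflict starts at Cycle 2. The every-other-week rule and the pre-cycle plus Day 15 rule are the same 14-day interval in a 28-day cycle.

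**Tests per cycle from Cycle 2.** Appendix I gives 1; Section 11.2.4 and footnote m give 2. The difference is 2 − 1 = 1 test per cycle. Footnote v of the schedules gives pomalidomide up to Cycle 24, so the most tests that could be omitted for one woman is 24 − 2 + 1 = 23.

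**Longest delay in detection.** The next test under Appendix I falls before Day 1 of the next cycle, which is Day 29 of the current one: 29 − 15 = 14 days.

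**Most additional dosing before detection**, taking Day 15 as the first dose that a positive test would have stopped:

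- Pomalidomide, Days 15–21: 21 − 15 + 1 = 7 doses.
- Oprozomib 5/14, Days 15–19: 19 − 15 + 1 = 5 doses.
- Oprozomib 2/7, Days 15, 16, 22 and 23: 4 doses.

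These are ceilings. A pregnancy that becomes detectable only after Day 15 is found at the same pre-cycle test under either rule.

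**The case against.** The mismatch itself is not in dispute; its weight is.

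- **Appendix I stands alone.** Section 11 points to the schedules for test timing, and a site testing every 14 days also satisfies the 28-day rule. This shows which text to correct. It does not tell a site that Appendix I must yield, and the protocol has no precedence clause.
- **Section 10.6.1.1 and Appendix J lean toward the 14-day rule.** Both reserve the longer interval for regular cycles. That is fair. They do not support Appendix I, but they do not name absent menses either, so they leave the question open.
- **Other safeguards exist.** Contraception is confirmed at each visit, counselling is repeated at least every 28 days, only one cycle of pomalidomide is dispensed at a time, and a test precedes every cycle. These confine the consequence to part of one cycle, as the dose counts show. They do not replace the Day 15 test.
- **The group is narrow.** Section 6.1 exempts surgically sterilized women and postmenopausal women over 45 without menses for at least 2 years. This stands, and the number remaining is unknown.
- **The Day 14 test after discontinuation is new for this group.** Correct: neither Section 11.2.4 nor footnote m requires it. It follows from Appendix I's own rule for irregular cycles once the group is moved.
- **Amendment 3 was approved but not implemented.** This reduces the practical value of an edit. The Amendment 3 summary of changes lists no change to these testing rules, so the conflict probably existed in the active version too. That is an inference, because the summary shows only significant changes.

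**Conclusion.** The protocol contradicts itself, and Appendix I is the text to correct. From Cycle 2, a site following it would omit one required test per cycle for each woman of childbearing potential without menses. The worst case is detection 14 days later, with 7 further pomalidomide doses and 5 (5/14) or 4 (2/7) further oprozomib doses. These bounds assume 28-day cycles that start on time, full dosing, and a Day 15 result acted on before that day's doses. The 23-test ceiling further assumes treatment through Cycle 24. The size of the affected group cannot be estimated from the documents. This is a subject-safety and consistency point that should be fixed; it does not affect the DLT assessment, endpoints, sample size or any planned analysis.

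**What to change.** In the Appendix I rule for female subjects during study participation, make two edits:

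1. Limit the 28-day group to women with regular cycles by deleting the reference to no cycles.
2. Extend the 14-day group from irregular cycles to irregular or absent cycles.

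Add 'or absent' to the irregular-cycle wording in Section 10.6.1.1 and Appendix J so that every location states the same rule.

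The cost is a few words in three places. On study, the edits add no test beyond those already required by Section 11.2.4 and the schedules. After discontinuation they add one Day 14 test for this group.
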